10.3.3. Temporary Discontinuation of the Investigational Products

The administration of the investigational product should be continued as much as possible. If the investigational product is discontinued, the Investigator should determine whether the drug can be only temporarily discontinued. The permanent discontinuation should be the last decision.

If the Investigator considers the corresponding adverse event onset is not related to the investigational product according to his/her best medical judgment, the re-challenge of the investigational product will be conducted under the careful and adequate clinical/laboratory monitoring.

The Investigator should record all the temporary discontinuation and re-challenge dates on the appropriate page of the eCRF.

10.3.4. Discontinuation From Therapy or Assessment

A premature discontinuation will occur when a subject who signed informed consent ceases participation in the study, regardless of circumstances, before the completion of all study visits. Subjects can be prematurely discontinued from the study for one of the following reasons:

- **Nonfulfillment of inclusion/exclusion criteria (Screening Failure):** This reason applies if a patient is found not eligible for randomization at Screening (Visit 1) or at Baseline (Visit 4) before randomization. Screening failure subjects can be rescreened at any time after signing the informed consent form, and they will be given a new screening number.
- **An AE:** If a subject experiences an AE, premature discontinuation will be at the discretion of either the Investigator or the subject, independent of the event's relationship to the study treatment. The appropriate AE eCRF page must be completed.
- **Lack of efficacy:** This reason applies if response to the treatment is considered by the Investigator or the subject to be unsatisfactory.
- **Protocol noncompliance:** Any protocol violations detected during the trial should be corrected when possible and the subject allowed to continue. ONLY those violations that could affect the subject's safety (eg, illness requiring treatment[s] that in the clinical judgment of the Investigator [or after discussion with the medical monitor or the Sponsor] might invalidate the trial by interfering with the allocated double-blind study drug) or the willingness of the subject to comply with the study activities should lead to discontinuation.
- **Subject's request:** The subject is permitted to stop his/her participation at any time during the study without incurring any loss of his/her medical care. The Investigator should ensure that such withdrawal is not due to AEs or lack of efficacy, in which case those reasons should be selected.
- **Lost to follow-up:** Subjects who cannot be contacted and who do not have a known reason for discontinuation (e.g., withdrew consent or adverse event) will be classified as 'lost to follow-up' as the reason for discontinuation. In these cases, every effort should be made by the Investigator to ascertain the reason and to ensure the subject's attendance as soon as possible.

In case of withdrawal or discontinuation, unless informed consent has been withdrawn, the Investigator should make efforts to evaluate the withdrawal visit for all the subjects, together with a narrative description of the reason(s) for removing the subject, must be recorded in the source documents. The eCRF must document the primary reason for withdrawal or discontinuation.

10.3.5. Replacement Procedures

The subjects who were discontinued at the screening after signing the informed consent form can be re-screened in this study if they were not yet randomized. At this time, they must sign a new informed consent form.

If the randomized subject is withdrawn, he/she is not replaced with a new subject. The withdrawn subject's randomization number cannot be used again and the subject in question cannot participate in this study again.

10.4. TREATMENTS

10.4.1. Treatments Administered

The study drug will be provided by the Sponsor. During the study, patients will be supplied with Pre-filled Syringe (PFS) containing either PDA10 or Eprex[®]. All the PDA10 PFSs and Eprex[®] PFSs will have the same external appearance and will function in the same method.

After having been given full explanation about this study, the subject will sign the informed consent form. If the subject satisfies the inclusion/exclusion criteria at Screening (Visit 1), he/she will be administered Eprex[®] with iron supplement (if applicable) for 12 weeks. If the subject's hemoglobin level is within the target range (10.0 to 12.0 g/dl) at Baseline period (or observation period), he/she will be randomized to either PDA10 or Eprex[®] group at Baseline Visit. The subject randomized to either group will be treated with the investigational product for 28 weeks from the randomization in a double blind fashion.

Subjects who complete at Week 28 will be offered continuation of PDA10 treatment with iron supplement (if applicable) by entering the open-label extension phase. Subjects must complete the Week 28 (Visit 11) assessments before entering the open-label extension phase. Visit 11 at Week 28 of the maintenance phase will serve as the entry visit for the open-label extension phase.

- **Investigational product (PDA10 2,000 IU, PFS)**
- **Reference product (Eprex[®] 2,000 IU, PFS)**

In patients on hemodialysis, PDA10 or Eprex[®] will be administered as an IV bolus 1-3 times in a week. While the administration of PDA10 or Eprex[®] is independent of the dialysis procedure, PDA10 or Eprex[®] may be administered into the venous line at the end of the dialysis procedure to obviate the need for additional venous access. Alternatively, a bolus injection may be given during the dialysis session through a suitable venous port in the dialysis line.

Note:

1. The subcutaneous route of administration must not be used.
2. The maximum dosage should not exceed 300 IU/kg /dose.

Each site will be required to prepare, sign and retain a written delegation log signed by the PI for ensuring that the double-blind nature of the study is maintained.

10.4.2. Identity of Investigational Product(s)

The Sponsor will provide the study drugs packaged in a double-blind configuration in labeled containers and each subject's study drug will consist of either PDA10 or Eprex[®] during the maintenance phase. Each study center will be provided with drug supplies corresponding to a sequence of randomization numbers.

The properties of the investigational product provided by the Sponsor are listed in the table below.

PDA10 for intravenous injection is supplied in a pre-filled syringe (PFS).

Investigational Products	Appearance
Investigational Product: PDA10	Formulated as a sterile, colorless liquid in an isotonic sodium chloride/ sodium phosphate buffered solution in pre-filled syringe
Reference Product: Eprex [®]	Formulated as a sterile, colorless liquid in an isotonic sodium chloride/ sodium phosphate buffered solution in pre-filled syringe

Storage conditions

PDA10 and Eprex[®] are to be stored between 2°C and 8°C in the refrigerator, away from the freezer compartment and kept in the original carton. This temperature range should be closely maintained until administration to the subject.

The product should not be used, and discarded

- if the seal is broken,
- if the liquid is colored or particles floating is observed,
- if it may have been accidentally frozen, or
- if there has been a refrigeration failure

Note:

The investigational products should be visually inspected for particulate matter and discoloration prior to administration. Product exhibiting particulate matter or discoloration must not be used. The PFSSs should not be shaken; shaking may denature the glycoprotein, rendering it inactive.

The investigational products contain no preservatives, and the syringe should not be reused and unused portion must be discarded.

IV Injection should be administered over 1-2 minutes. In subjects on dialysis the injection should follow the dialysis procedure. Slow injection over 5 minutes may be beneficial to those who experience flu-like symptoms.

10.4.3. Method of Assigning Subjects to Treatment Groups

At the time of the Baseline Visit, patients will be randomly assigned to receive either PDA10 or Eprex[®] according to the interactive web response system (IWRS) upon signing the ICF. This randomization number will consist of two parts as follows:

2-digit unique investigational site number established by Pangen Biotech

2-digit patient screening number consisting of sequential patient number unique within a site

For example, for a study center with number 99, the first consented patient 01 would have the following screening number 99S01 and the first randomized patient would have the following randomization number 99R01

The randomization number will be used to identify the subject throughout the study and will be recorded on the eCRF. This number must not be reused. Subjects who are rescreened will receive the next available randomization number to avoid confusion with data from the previous screenings.

10.4.4. Selection of Dosages in the Study

1) Observation period

In order to evaluate the Hb level of patients for screening, patients will be monitored on the Eprex[®] dosage previously treated for four weeks from screening visit and the Hb levels will be monitored every 2 weeks. When the Hb level and iron status meet the following criteria, the patients will proceed to the maintenance phase or the titration phase.

- **Criteria to proceed the maintenance phase without titration phase**

Patients on Eprex[®] treatment for at least 12 weeks and with hemoglobin within the target range of 10.0 to 12.0 g/dl and a stable IV dose of Eprex[®], and adequate iron store (serum ferritin level \geq 100 ng/mL and/or transferrin saturation \geq 20%) during observation period will proceed to enter the maintenance phase. Hb level measured during this observation period will be considered as baseline level.

- **Criteria to proceed the titration phase**

- 1) Patients treated with other EPO products for at least 12 weeks

If the patients are treated with other EPO products, the patients should proceed to the titration phase to exposure the Eprex[®] for at least 12 weeks.

- 2) Hb is below 10 g/dL even if the patients were treated with Eprex[®] for at least 12 weeks; in the event a patients' Hb is to decline below 10 during the observation period, patients should switch to titration phase.

2) Titration phase

The initial dosage of Eprex[®] will be the same with the erythropoietin dosage previously treated. However, the increased dosage will be treated for the initial dosage if Hb level is less than 10 g/dl prior to Screening Visit. The Hb level of patients is monitored every 2 weeks during titration phase. Eprex[®] dose changes will be made every four weeks on the basis of the most current Hb level—more frequent changes will be made only when the Hb value or the rate of Hb change is outside the preset safety as follows;

- If Hb level increase in the past two weeks is > 1.0 g/dL or Hb level is approaching 12 g/dL, the dose will be decreased by 25% of current dosage. If the hemoglobin continues to increase or exceed 12 g/dl, the treatment should be temporarily withheld until the hemoglobin begins to decrease, at which point therapy should be reinitiated at a dose approximately 25% below the previous dose. If dose reduction is needed, the amount given per dose or the number of weekly injections will be reduced, or both will be reduced.
- If Hb level increase in the past two weeks is < 0.3 g/dL and Hb level is below 10 g/dL, the dose will be increased by 25% of current dosage.
- If Hb increase in the past 2 weeks is ≤ 1.0 g/dL and Hb level is in the target range (10 – 12 g/dL), the dose will be maintained.

When a change in Eprex[®] dose is indicated, a one-step change (25% of current dosage) is performed based on the stepwise dosing schedule refer to appendix III.

* The patients will be treated with iron therapy based on iron level as follows;

- ① Marginal iron store (all patients will have serum ferritin level > 100 to be eligible for entry) -

Eprex[®] dose increasing during the titration phase and IV iron as appropriate. For patients unable to access IV iron therapy, sponsor will support the iron therapy.

- ② Hb is below 10 g/dl and serum ferritin level > 500 - Eprex[®] dose increasing during the titration phase and a close iron monitoring. If serum ferritin is to decline rapidly, giving IV iron should be considered appropriately. For patients unable to access IV iron therapy, sponsor will support the iron therapy.

During last four weeks of the titration period, the Hb level will be evaluated to meet the inclusion criteria to conduct the randomization as same as observation period. Patients with stable Hb maintained between 10 and 12 g/dl and on stable Eprex[®] dose will proceed to enter the maintenance phase at the end of the titration period. The last four weeks of the titration phase will be considered the baseline period, and Hb levels measured during baseline period will be considered as baseline level.

3) Maintenance Phase:

The IV dose has to be adjusted individually to maintain hemoglobin between 10 - 12 g/dl. The hemoglobin, hematocrit, and dose will be monitored every two weeks during the maintenance phase. Investigators will decide to change or maintain the dosage of Eprex[®] or PDA10 every four weeks based on Hb level. The dosage will be determined according to the dose adjustment scheme below, and if hemoglobin level is not increased by more than 1 g/dl in any 2-week period or is not approaching 12 g/dl or below 10 g/dl, the dose will be maintained. The maintenance dose should be individualized, and the recommended total weekly dose should not exceed 300 IU/kg.

Suggested Target Hemoglobin level Range:

10 g/dl to 12 g/dl

During the study, Hb, Hematocrit and dose of Eprex[®] or PDA10 will be monitored every two weeks. Prior to and during the study, the patient's iron stores, including transferrin saturation (serum iron divided by iron binding capacity) and serum ferritin, will be evaluated.

Dose Adjustment Scheme:

If the hemoglobin increases by more than 1 g/dl in any 2-week period or the hemoglobin is approaching 12 g/dl, the dose should be reduced by approximately 25%. If the hemoglobin continues to increase or exceed 12 g/dl, the dose should be temporarily withheld until the hemoglobin begins to decrease, at which point therapy should be reinitiated at a dose approximately 25% below the previous dose. If dose reduction is needed, either the amount given per dose or the number of weekly injections will be reduced, or both will be reduced.

If the hemoglobin is below 10 g/dl, the dose may be increased by approximately 25% of the previous dose.

When a change in Eprex[®] or PDA10 dose is indicated, a one-step change (25% of current dosage) is performed according to the stepwise dosing schedule refer to appendix III.

The dose adjustment scheme in Open-Label Extension phase is same as maintenance phase, but hemoglobin will be assessed every 4 weeks.

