APPENDIX II. IRON STATUS AND THERAPY

	Hb, Epoetin and iron status	Hb, Epoetin and iron management during titration phase
1	Hb in target range (10 to 12 g/dl) and adequate iron store (serum ferritin level > 100)	
Continue on usual Epoetin dose and observe Hb for 4 weeks. Patients with stable Hb maintained between 10 and 12 g/dl, and on stable Epoetin dose will proceed to enter the maintenance phase at the end of the baseline period.
 
Hb levels measured during this observation period will be considered as baseline level.
 
In the event a patient's Hb were to decline below 10 g/dl during the observation period, patients should switch to titration phase as described below

2	Hb below target range (< 10) and marginal iron store (all patients will have serum ferritin level > 100 to be eligible for entry)	
Increase Epoetin dose during titration phase, and give IV iron as appropriate.
 
For patients unable to access IV iron therapy, sponsor will support the iron therapy.

3	Hb below target range (< 10) and serum ferritin level > 500	
Increase Epoetin dose during titration and monitor iron closely. If serum ferritin were to decline rapidly, giving IV iron should be considered appropriately.
 
For patients unable to access IV iron therapy, sponsor will support the iron therapy.

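### In titration, a patient with Hb below 10 g/dl, marginal iron or ferritin above 500, and a two-week Hb rise above 1.0 g/dl is directed both to a lower and to a higher epoetin dose

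*Protocol*

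**What the plan says.** Four places in the protocol bear on the dose of a patient with low Hb in the titration phase.

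**Section 10.4.4, titration bullets** (repeated in the synopsis under Dosage). Three rules use the two-week change in Hb:
- Decrease by 25%: "If Hb level increase in the past two weeks is > 1.0 g/dL or Hb level is approaching 12 g/dL, the dose will be decreased". The first trigger has no lower Hb limit.
- Increase by 25%: "If Hb level increase in the past two weeks is < 0.3 g/dL and Hb level is below 10 g/dL".
- Maintain: "If Hb increase in the past 2 weeks is ≤ 1.0 g/dL and Hb level is in the target range", the target range being 10 to 12 g/dl.

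The bullets follow a sentence saying that changes are normally made every four weeks on the latest Hb, and that more frequent changes need a trigger.

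**Section 10.4.4, iron notes** (also in the synopsis). Note 1 covers marginal iron stores and gives a rising Eprex dose in titration, with no Hb condition. Note 2 gives the same for "Hb is below 10 g/dl and serum ferritin level > 500". Neither mentions the rate of rise.

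**Appendix II.** The right-hand column is headed as Hb, epoetin and iron management in the titration phase. Row 2 (Hb below 10, marginal iron) says "Increase Epoetin dose during titration phase, and give IV iron as appropriate". Row 3 (Hb below 10, ferritin above 500) says "Increase Epoetin dose during titration and monitor iron closely". Neither has a condition on the rise.

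**Appendix III.** This gives the dose ladder that turns a 25% step into a weekly dose.

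**The concern.** One set of instructions makes the dose depend on how fast Hb is rising; the other does not. Where they overlap, a site can follow the protocol and move the dose in either direction, depending on which page it has open.

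The overlap falls where the protocol itself sees risk. Section 7.4 regards a rise of about 1 g/dl per month as sensible for most patients and says that exceeding it may raise the risk of adverse events. A rise above 1.0 g/dl in two weeks, if sustained, is more than 2.0 g/dl in four weeks, over twice that pace.

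About 20 centres in two countries are planned (Section 6), so different readings between sites are foreseeable.

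**Working it through.** No sample-size, power or error-rate figure depends on this point. The check sets the instructions side by side for a patient in titration with Hb below 10 g/dl who falls in Appendix II row 2 or row 3.

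| Two-week rise (g/dl) | Example Hb | 10.4.4 bullets | Appendix II rows 2 and 3, iron notes | Result |
|---|---|---|---|---|
| below 0.3 | 9.6 to 9.7 (+0.1) | increase 25% | increase | agree |
| 0.3 to 1.0 | 9.2 to 9.7 (+0.5) | no bullet applies | increase | gap against instruction |
| above 1.0 | 8.6 to 9.8 (+1.2) | decrease 25% | increase | opposite directions |

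In the middle band the increase bullet fails because the rise is not below 0.3, the decrease bullet fails because it is not above 1.0, and the maintain bullet fails because Hb is not in 10 to 12.

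**Size of the opposite-direction case.** Take the Appendix III row for 4,000 IU/week:
- one step down: 4,000 − 1,000 = 3,000 IU/week
- one step up: 4,000 + 1,000 = 5,000 IU/week
- ratio: 5,000 / 3,000 = 1.67, a 67% difference at a single decision.

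**Who is covered.** Row 2 needs a marginal iron store, a term the protocol does not define; row 3 needs ferritin above 500. A patient with Hb below 10 and non-marginal ferritin up to 500 is in neither row. For that patient there is no conflict above 1.0, although the gap at 0.3 to 1.0 remains.

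**A second mismatch.** Iron note 1 lacks the Hb-below-10 condition that Appendix II row 2 carries. Read literally, a patient with marginal iron, Hb in 10 to 12 g/dl (and not approaching 12) and a rise of at most 1.0 g/dl is told by the bullet to keep the dose and by the note to raise it.

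**Precedence.** No sentence in 10.4.4, the synopsis or Appendix II says which instruction governs, or limits rows 2 and 3 to the start of titration.

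**The case against.** The best defence is that Appendix II is not a rival visit-by-visit algorithm. Its title concerns iron, it gives no step size or interval, and row 1 passes patients whose Hb falls below 10 during observation on to the titration instructions beneath it. Rows 2 and 3 could therefore describe only the step on entering titration. That would fit 10.4.4, which already raises the initial dose when Hb was below 10 before screening. The reading is possible, but the text does not state it: the column heading and both rows speak of the titration phase as a whole, and 10.4.4 has its own separate sentence on the entry dose. The ambiguity stands.

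Three stronger readings are tempting and are not supported.

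- **That 10.4.4 allows an increase only if the rise is below 0.3.** The bullets are introduced as triggers for changes more often than every four weeks, and routine changes rest on the latest Hb. At 0.3 to 1.0 the section is silent, not contrary.
- **That the entry dose could differ two-fold.** Three steps up the ladder (4,000, 5,000, 6,000, 8,000) do double the dose. But this assumes that a site following the bullets would hold at 4,000, which no bullet says for Hb below 10. In the 12-week schedule the decisions fall at Weeks −12, −8 and −4. The Week −12 step is no divergence if Hb was below 10 before screening, since 10.4.4 raises the initial dose too. A third increase needs Hb below 10 at Week −4, which is a baseline measurement; randomisation requires Hb of 10 to 12 over the baseline period, so that patient could enter only after a prolonged titration.
- **That the conflict distorts the baseline and so the dose co-primary comparison.** Titration precedes randomisation and everyone receives Eprex. Randomisation is stratified by country and site (10.4.5), the ANCOVA includes centre and baseline value (10.6.4.1), and a stable dose is an entry requirement. Different titration habits between sites do not favour an arm.

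**Conclusion.** The conflict is real but narrow. It is a direct contradiction for patients in titration with Hb below 10 g/dl, a two-week rise above 1.0 g/dl, and either marginal iron or ferritin above 500. It rests on taking rows 2 and 3 and the iron notes at their word, as applying throughout titration; if the sponsor meant them only for entry, the protocol needs to say so. The unaddressed 0.3 to 1.0 band and the missing Hb condition in iron note 1 are lesser defects in the same text.

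The firm size is the single-decision gap from 4,000 IU/week. The documents do not say how often such a patient would occur, so no overall frequency can be given. What is at stake is patient safety in a fast-rising patient and consistent titration across centres. Neither the equivalence test nor the balance between arms is affected.

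**What to change.** Reconcile the 10.4.4 titration bullets, the two iron notes, the matching synopsis text and Appendix II so that one instruction applies to Hb below 10 g/dl in titration for each band of two-week rise: below 0.3, 0.3 to 1.0, and above 1.0 g/dl. State how Appendix II and the iron notes relate to the bullets, including whether rows 2 and 3 apply only on entering titration. Align the Hb condition in iron note 1 with that in row 2. The sponsor's clinicians decide the content of the rule.

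The cost is protocol wording in these places. No assessment, visit or analysis changes.

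### Titration iron rule, item 1, raises the Eprex dose on marginal iron alone, against the hemoglobin-based dosing rules and Appendix II

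*Protocol*

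**What the plan says.** Protocol section 10.4.4, part 2 (Titration phase), first sets the epoetin rule by hemoglobin: "dose changes will be made every four weeks on the basis of the most current Hb level". Three bullets follow.

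- First bullet: if Hb rose by more than 1.0 g/dL in two weeks, or "Hb level is approaching 12 g/dL, the dose will be decreased by 25% of current dosage". Treatment is withheld if Hb keeps rising or exceeds 12.
- Second bullet: if the two-week rise is below 0.3 g/dL and "Hb level is below 10 g/dL, the dose will be increased by 25% of current dosage".
- Third bullet: if the two-week rise is at most 1.0 g/dL and "Hb level is in the target range (10 – 12 g/dL), the dose will be maintained".

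A two-item list on iron therapy comes next. Item 1 has a single trigger, marginal iron store, and its action is "Eprex[®] dose increasing during the titration phase and IV iron as appropriate". Item 2 has the trigger "Hb is below 10 g/dl and serum ferritin level > 500". The Synopsis (Dosage, Titration phase) repeats both items, again with no Hb condition in item 1.

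Appendix II gives the same iron rules as a table. Row 2 is headed "Hb below target range (< 10) and marginal iron store" and its action is an epoetin increase with IV iron as appropriate. Row 1 covers Hb 10 to 12 with ferritin above 100 and says "Continue on usual Epoetin dose and observe Hb for 4 weeks".

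**The concern.** Item 1 appears to have lost the Hb condition that its counterpart in Appendix II carries. Read as written, it raises epoetin in a patient who is already in the target range, possibly with IV iron added, which section 10.2 describes as epoetin-sparing. Section 7.4 explains why that is undesirable: it places the best balance of risk and benefit at 10 to 12 g/dl and links too fast an Hb rise to adverse events. The practical risks are Hb overshoot, withheld doses, a dose too unstable for randomization, and prolonged titration.

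**Working it through.** The protocol gives no figure for this point, so the main check sets the rules side by side. For a titration patient with marginal iron:

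| Hb state | Iron item 1 | Hb bullets | Appendix II row 2 |
|---|---|---|---|
| Below 10, two-week rise below 0.3 | Increase | Increase | Increase |
| Below 10, two-week rise 0.3 or more | Increase | No increase called for | Increase |
| 10 to 12, rise at most 1.0 | Increase | Hold | Not triggered |
| Approaching 12, or rise above 1.0 | Increase | Cut 25% | Not triggered at Hb 10 or above |
| Still rising, or above 12 | Increase | Withhold | Not triggered at Hb 10 or above |

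At any Hb of 10 or more, item 1 contradicts the bullets, and Appendix II does not support it.

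**Can an in-range patient be in titration?** Yes. Section 10.4.4, part 1, sends patients on other epoetin products to titration with no Hb condition. Patients who start below 10 are also meant to reach the range during this phase.

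**When would item 1 be triggered?** Section 10.5.3.4 schedules iron tests before randomization only at Visits 1 and 4. On the standard schedule the screening result would be the trigger.

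**How large is one unneeded step?** From Appendix III, percent change = (new − old) / old.

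| Weekly dose (IU) | After increase | Change | After decrease | Change |
|---|---|---|---|---|
| 2,000 | 3,000 | +50.0% | 1,000 | −50.0% |
| 3,000 | 4,000 | +33.3% | 2,000 | −33.3% |
| 4,000 | 5,000 | +25.0% | 3,000 | −25.0% |
| 5,000 | 6,000 | +20.0% | 4,000 | −20.0% |
| 6,000 | 8,000 | +33.3% | 4,000 | −33.3% |
| 7,000 | 9,000 | +28.6% | 5,000 | −28.6% |
| 8,000 | 10,000 | +25.0% | 6,000 | −25.0% |
| 9,000 | 11,000 | +22.2% | 7,000 | −22.2% |
| 10,000 | 12,000 | +20.0% | 8,000 | −20.0% |
| 11,000 | 14,000 | +27.3% | 8,000 | −27.3% |
| 12,000 | 15,000 | +25.0% | 9,000 | −25.0% |

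Increases run from 20% to 50%. Five of the 11 steps in each direction exceed 25%.

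**What does the correction do?** Inclusion criterion 7 (section 10.3.1) allows at most a 25% change in weekly dose over the baseline period. One step up followed by one corrective step down gives:

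- 2,000 → 3,000 → 2,000: final cut (2,000 − 3,000) / 3,000 = −33.3%
- 5,000 → 6,000 → 4,000: final cut (4,000 − 6,000) / 6,000 = −33.3%
- 9,000 → 11,000 → 8,000: final cut (8,000 − 11,000) / 11,000 = −27.3%

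The six other starting doses with a listed step-down row give final cuts of 20% to 25%. The increases to 14,000 and 15,000 IU have no row to step down from. A cut above 25% fails the criterion only if it falls in the last four weeks of titration.

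**The case against.** The best defense is that epoetin dosing is already governed by Hb. The section says so before the three bullets. Item 1 sits under a separate lead-in about iron therapy and is a clipped phrase, and section 10.2 refers sites to Appendix II, where the condition is complete. A site would have to override all of that to be misled. This makes harm less likely, and many investigators would follow the Hb rules. It does not settle the conflict: item 1 itself directs a dose increase, it stands in the dosing section and again in the Synopsis, and no sentence says which text prevails. The qualifier at the end of item 1 reads most naturally with IV iron only.

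A second objection is that the affected group is undefined. Marginal iron has no cut-off, and item 1 notes that entrants have ferritin above 100, which Appendix II row 1 calls adequate. It stands to this extent: the number of in-range patients affected cannot be derived. The missing cut-off does not make the group empty; it leaves the site to decide who belongs in it.

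A third objection concerns timing and scale. An increase triggered at Week -12 would probably be corrected before the baseline period, given two-weekly Hb checks and titration extendable to 20 weeks. The step sizes also belong to Appendix III and apply to correct Hb-driven changes too. Both points are fair. The stability failure is a possibility, not a forecast, and the percentages describe what one unneeded step does, not how often it happens.

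**Conclusion.** The concern holds. The current wording of item 1, in section 10.4.4 and the Synopsis, contradicts the Hb-based titration bullets for every patient with marginal iron and Hb of 10 g/dl or more. It also departs from Appendix II row 2, and a dropped clause is the likely cause.

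The per-patient size is one unneeded increase of 20% to 50% in weekly dose. For three of the nine starting doses that can be traced up and back down, the correcting cut exceeds 25%. The conclusion assumes only that item 1 is followed as written; the frequency is unknown.

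The consequence is limited to safety and a stable baseline before randomization. Two-weekly Hb monitoring and the withholding rule contain it. No effect on the comparison between arms, the margins or the sample size is claimed. As an operative dosing instruction that conflicts with the protocol's own rules, it should be corrected.

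**What to change.** In item 1 of the titration iron rule, in both section 10.4.4 and the Synopsis, add Hb below 10 g/dl as a condition alongside marginal iron store, as in Appendix II row 2. Add one sentence stating that the Hb-based titration bullets determine the epoetin dose. A patient with Hb 10 to 12 and marginal iron then receives IV iron as appropriate, with the dose held or cut by those bullets. The sentence also settles the case of Hb below 10 that is already rising by 0.3 g/dL or more in two weeks, where the iron rule and the bullets differ too.

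The cost is one clause in two places and one sentence, by amendment. No new data, visits or patients are needed.
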